Protocol Title: Endovascular Embolization for Chronic Subdural Hematomas Following Surgical Evacuation

Principal Investigator: [name]

1. Objectives

Describe the purpose, specific aims, and hypothesis:

Evaluate the effectiveness of endovascular embolization of the middle meningeal artery following surgical evacuation of subdural hematomas (SDH) to assess rate of recurrence of SDHs.

2. Background

Describe the background and rationale for the study:

The historical standard for treatment of chronic subdural hematomas (SDH) has been through surgical evacuation through burr holes or craniotomies. Many of these patients are elderly patients who are high risk surgical candidates. Unfortunately given the pathophysiology of SDHs there is a high rate of recurrence ranging 5-30% in the literature necessitating frequent imaging, increased length of hospital stay, increased morbidity, and increased rate of reoperations. A more novel and less invasive approach has been used to treat SDHs in this patient population. There are increasing reports of endovascular embolization of the middle meningeal artery using a less invasive endovascular approach for SDHs. The reported outcomes in literature have been very positive when endovascular embolization has been used without surgery or as an adjuvant to surgery. These reports include case series and retrospective reviews. There have been no studies directly comparing endovascular embolization following surgical evacuation to assess if this technique can actually benefit patients with chronic SDHs. We propose to study this treatment process by randomly assigning patients who have undergone surgical evacuation of SDHs through burr holes into a control and treatment group. The control group (surgery) would only receive surgical evacuation of a hematoma using current standard of care. The treatment group (surgery plus) would receive surgical evacuation followed by endovascular embolization of the middle meningeal vessels using current standard of care. We will directly compare these two treatment modalities to obtain class I evidence on the efficacy of embolization for treatment of chronic subdural hematomas.

References:

All procedures done during the course of this study are standard treatments for SDH. Patients with SDH that require surgical evacuation who agree to participate, will be randomly assigned either to a surgery group who will continue their course of care after surgery with no further intervention (unless needed as determined by standard of care) and a surgery plus group who, after surgery, will undergo endovascular embolization using standard of care embolization procedures (unless embolization is not indicated for the patient as determined by standard of care). Embolization includes cerebral angiogram with polyvinyl alcohol particle or onyx glue embolization via a catheter inserted in the groin while under general anesthesia. Patients undergoing SDH surgical evacuation are hospitalized on average 2-5 days; randomization and the embolization procedure will take place during the same hospitalization period within 72 hours after surgery. Embolization is a minimally invasive procedure and patients are typically discharged on post procedure Day 1, so the hospital stay will not be increased due to the embolization procedure. Patients will undergo a CT scan within 24 hours after surgery. This scan is standard care and will occur prior to the embolization. Approximately 4-6 weeks after the hospitalization, the patients will undergo a standard follow-up CT scan. Further scans will be done thereafter if clinically indicated. All patients will have the same follow-up care during the course of their hospitalization unless there is a complication.

These procedures, surgery and embolization, are done routinely separately and in combination for treatment of SDH. The research procedure will be the collection of data from these patients to assess whether endovascular embolization following surgical evacuation can reduce the complications of SDH.

b. Describe and explain the study design:

If the study involves multiple conditions where each condition involves different procedures, please provide a table that breaks down the procedures by condition and in chronological order. Include when and where they are performed.

The study design will include a surgery group and a surgery plus group. All patients will have been scheduled to undergo surgical evacuation of SDH as standard treatment. These patients will be approached by one of the investigators with information about the study. After consent, the patient will be randomly assigned to either the surgery or the surgery plus group. A random number list will be provided to the investigators to use for assignment of patients to the surgery or surgery plus group. Patients randomized in the surgery plus group will subsequently undergo endovascular embolization within 72 hours after surgery and during their hospital stay. Patients in the surgery group will not undergo

the embolization procedure. CT scans will be performed as described above as standard care for this population. Follow-up care during their hospitalization will be the same for both groups barring a complication. All procedures (surgical evacuation and endovascular embolization) performed are standard treatment options for SDH that are used at our institution and facilities across the country

c. Data Types and Source Records:

Data will be collected from medical records and will include the following: name, medical record number, age, sex, GCS at admission, IPH volume, whether the patient had surgery, length of stay in the ICU and hospital, IPH volume post-operatively from CT scans, anticoagulant use, history of brain trauma, and any complications (AEs or SAEs).

The study information will be entered into spreadsheets and stored on the secure drive provided by Information Technology specifically for the study.

d. Describe the procedures performed to lessen the probability or magnitude of risks

All data will be managed in a secure format and according to all applicable regulatory guidelines. All medical records information will be entered into the secure drive by the PI or designated study team members. There will be a separate key to link the entries on the data collection form using an assigned study ID# and the patient medical records. The key will be stored on the secure drive. Only the approved investigator or study team members with username/password access will review medical records and the study information that is collected and stored on the secure drive. Women of child-bearing potential are routinely assessed for pregnancy during the pre-operative workup; any with a positive pregnancy test will not be considered for the study, either as treatment or control subjects. Endovascular embolization and imaging are approved and widely used standard treatment options for SDH but carries the risks of groin hematoma, infection, and embolic stroke. In the event of groin hematoma, pressure is applied to the site, evidence of infection would be treated with appropriate antibiotics, and the AU acute stroke protocol would be implemented in the event of an embolic stroke. Study investigators are experienced in performing the procedure and caring for the patients.

If the patient's clinical picture indicates that the embolization procedure is necessary, the patient would not participate in the study. If this determination is made following consent, the patient would be considered a screen failure.

e. Describe the duration of an individual subject's participation in the study and the time involved also include the overall duration of the project:

The duration of subject participation may range from 2 weeks to 3 months following surgical intervention. These are typical follow-up timelines for patients undergoing treatment for SDH. Study information collected from medical records will extend from the time of diagnosis until the completion of follow-up visits.

9. Data and Specimen Management


a. Describe the data analysis plan, including any statistical procedures:
 
Data analysis will include patient age and sex, GCS score, need for redo surgery for surgical decompression of SDHs, complication rates of procedures, length of hospital stay, and follow up CT imaging findings, anticoagulant use, and history of brain trauma. All statistical analysis will be performed using SAS 9.4 and statistical significance will be assessed using an alpha level of 0.05. Descriptive statistics will be determined within surgical group (treatment or control) and will include frequencies and percentages for categorical variables, means and standard deviations for continuous variables, and medians and interquartile ranges for ordinal data.
 
To examine differences in the need for additional surgical decompression of SDH, demographic variables, CGS scores, complication rates of procedures, length of hospital stay, and follow up CT image findings a variety of statistical tests will be performed. For categorical data (additional surgical decompression of SDH, sex, complication rates of procedures, and follow up CT image findings), chi-square tests will be used to examine differences in proportions between control and treatment groups. For continuous data (age, GCS score, and length of hospital stay) two-sample t-tests will be used to examine differences in means between control and treatment groups. For the mRS score, a non-parametric Wilcoxon Rank Sum test will be used to examine differences in medians between control and treatment groups.
	 N/A																				

b. When applicable, provide a power analysis:
 
The sample size needed to examine differences in percent needing additional surgical decompression of SDH using a chi-square test at an alpha level of 0.05 was determined assuming a power of 0.80, 0.85 and 0.90. The percent needing additional surgical decompression of SDH in the control group was assumed to be 35%. The percent needing additional surgical decompression of SDH in the treatment group was assumed to be 5% and 10%. The table below shows the required sample size per group to detect differences in the percent needing additional surgical decompression of SDH between the treatment and control groups.
	N/A																				


Recurrence per Group	Sample Size per Group by Power	

Control	Treatment	Power=0.80	Power=0.85	Power=0.90	

35%	5%	27	31	36	

35%	10%	43	49	57	

	Recurrence per Group		Sample Size per Group by Power			Control	Treatment	Power=0.80	Power=0.85	Power=0.90	35%	5%	27	31	36	35%	10%	43	49	57	
Recurrence per Group		Sample Size per Group by Power																			
Control	Treatment	Power=0.80	Power=0.85	Power=0.90																	
35%	5%	27	31	36																	
35%	10%	43	49	57																	

The expected percent needing additional surgical decompression of SDH in the treatment group is expected to be 5% or lower. A sample size of 30 per group, for a total of 60 patients, will provide adequate power to show differences between these two groups.
																					

c. Describe how data and specimens will be handled:
	 N/A																				

i. What information will be included in that data or associated with the specimens?

Data to be assessed include: name, medical record number, age, sex, GCS at admission, IPH volume, whether the patient had surgery, length of stay in the ICU and hospital, IPH volume post-operatively from CT scans, anticoagulant use, recent brain trauma, and any complications (AEs and SAEs).

ii. Where and how data and/or specimens will be stored?

The data will be stored on a secure website provided by AU Information Technology specifically for this study that is accessible by approved team members using username/password access. The data collection form and the key to link the records will be stored separately on the secure drive.

iii. How long will the data and/or specimens be stored?

Data will be maintained according to AU and University System Board of Regents policies.

iv. Who will have access to the data or specimens?

Data access will be restricted to the research team

i. Who is responsible for receipt or transmission of the data and/or specimens?

The study investigators

ii. How will data and/or specimens be transported?

N/A

10. Provisions to Monitor the Data to Ensure the Safety of Subjects N/A

The plan might include establishing a data monitoring committee and a plan for reporting data monitoring committee findings to the IRB and the sponsor.

a. Describe the plan to periodically evaluate the data collected regarding both harms and benefits to determine whether subjects remain safe.

A Data Safety Monitoring Board will be established to assess harms and benefits to subjects. The DSMB will evaluate safety data every 6 months during the trial and at the reporting of any serious adverse event.

b. Describe what data are reviewed, including safety data, untoward events, and efficacy data.

The data collection form and all AEs and SAEs will be reviewed, including whether repeat surgery is needed, length of ICU stay and hospitalizations, and any complications/adverse events that occur.

c. Describe how the safety information will be collected (e.g., with case report forms, at study visits, by telephone calls with participants).

The information will be collected from medical records and entered into the data collection form and/or AE/SAE form.

d. Describe the frequency of data collection, including when safety data collection starts.
 
Data collection, including safety information, will begin as soon as patients are enrolled and will last up to three months post-procedure.

e. Describe who will review the data.
 
Members of the DSMB will include [name] and [name]. Both are board-certified neurosurgeons who have completed CITI training.

f. Describe the frequency or periodicity of review of cumulative data.
 
Every 6 months and at the report of any SAE.

g. Describe any conditions that trigger an immediate suspension of the research.
 
If the embolization procedure is associated with statistically significant increased risks to the subject

11. Withdrawal of Subjects

N/A

a. If applicable, describe anticipated circumstances under which subjects will be withdrawn from the research without their consent.
 
Physicians may determine that it is not in the best interest of the patient to undergo the embolization procedure; the patient would be removed for their safety. The patient may also be removed from the study if the physicians determine that another type of treatment would be more beneficial.
	 N/A

b. If applicable, describe any procedures for orderly termination.
 
The procedure would not be done.
	 N/A

c. If applicable, describe procedures that will be followed when subjects withdraw from the research, including partial withdrawal from procedures with continued data collection.
 
Subjects may choose to discontinue their participation in the study at any time by notifying the PI. To withdraw from the study individuals are asked to send a written letter to the PI. Data collection for the subject will stop, but data already collected will continue to be used. Subjects may, at any time, change their mind and decide not to have the embolization procedure by letting the study doctors know their wishes. If the embolization procedure is not done, the patient will be included in the analysis as they were randomized.
	 N/A

12. Risks to Subjects

a. List the reasonably foreseeable risks.

There is a potential risk in breach of confidentiality. Endovascular embolization is an accepted standard of care treatment for subdural hematoma but carries the additional risk of groin hematoma, infection, and embolic stroke. The risks of the procedure will be addressed with subjects randomized to the procedure. Control subjects will have no further risks associated with participation.

b. If applicable, describe any costs that subjects may be responsible for because of participation in the research.

The patient's insurance will be billed for the endovascular embolization procedure that is standard clinical care. The patient will be responsible for paying for the care they would normally receive for their condition, as well as for all co-pays, deductibles and denied claims. The embolization procedure and the surgery-embolization procedure combination have been standard practice for the last three years and insurance companies typically pay when both procedures are done in a single hospitalization.

N/A

c. If applicable, describe risks to others who are not subjects.

Click here to enter text.

X N/A

13. Potential Benefits to Subjects

Describe the potential benefits that individual subjects may experience from taking part in the research
There is no benefit guaranteed to the subjects. It is hoped that the results of this study will benefit patients in the future.

14. Confidentiality

Describe the procedures for maintenance of confidentiality.

All investigators have undergone proper training for evaluation and handling patient information through the CITI program. Only the study investigator and research staff with username/password access to the system will collect data from medical records. Study data will be stored on the secure drive requiring username/password access and will be available to only the study investigator and staff. The data collection form will contain no identifiable information. The original signed informed consent documents will be secured in a locked cabinet that is accessible only to members of the study team. No identifiable patient information will be used in any publication materials. All study information will be kept confidential per HIPAA regulations.

15. Incomplete Disclosure, Authorized Deception, or Deception

N/A

Click here to enter text.

16. Consent Process

The patient/legally authorized representative (LAR) will be approached in a private setting by an approved research team member to discuss the study. The study will be explained at a level they can understand. The patient/LAR will be given time to review the consent and it will be explained to them by the team member. The purpose of the study, nature of their involvement, risks, benefits, alternatives and confidentiality will be addressed. The subject/LAR will be told they do not have to participate in the study to have the embolization procedure done. Any questions will be addressed until the patient/LAR is satisfied. The consent/adult assent will be signed in the presence of the approved team member, a copy will be given to the patient/LAR and a copy will be filed in the subject's medical records. The patient/LAR will be given the opportunity to take the consent home to review with family or others if they wish.

Prior to the embolization procedure, cognitive capacity of the patient will have already been assessed by the neurosurgical service (third party not associated with the study) in an effort to obtain consent for surgical evacuation of the SDH. Based upon those findings, consent for the study will be obtained from the patient or the LAR, whichever is appropriate. The patient will be assessed for improvement or deterioration before study consent is obtained by means of a neurological exam.

In the event that a subject is deemed cognitively impaired or has impaired decision-making capacity, an LAR who will determine what is in the patient's best interest will be identified as follows:

- *An individual with durable power of attorney for health care*
- *Legal guardian*
Next of kin 18 years of age or older:
 - *Spouse*
 - *Child*
 - *Parent*
 - *Sibling*
 - *Grandparent*
 - *Grandchild*
 - *Close friend*

Based upon the investigator's assessment, the patient may be deemed able to provide meaningful assent, and every effort will be made by the investigators to review the assent document with the subject in a manner and language they can understand, explaining the purpose, procedures, risks and benefits, and assuring that the patients understands. If the patient provides assent, the LAR will also be used to provide consent. During the course of their participation, the subject will be re-assessed by the investigators to determine whether their decision-making capacity has changed and if consent/assent is possible. If a subject regains decision-making capacity and indicates they do not wish to participate, the subject will be withdrawn.

17. Compensation for Research-Related Injury

This section is not required when research involves no more than Minimal Risk to subjects. **N/A**

a. Describe the available compensation in the event of research related injury.

In the event that this research related activity results in an injury, treatment will be made available including first aid, emergency treatment, and follow-up care as needed. Cost for such care will be billed in the ordinary manner to the patient or the patient's insurance company. No reimbursement, compensation, or free medical care is offered by Augusta University.

18. Qualifications to Conduct Research and Resources Available

Describe the qualifications of you and your staff to conduct this research. The IRB is looking for information such as area(s) of expertise, past research experience, relevant certifications, etc.

For international research or research with vulnerable populations, describe the qualifications (e.g., training, experience, oversight) of you and your staff as required to conduct the research. When applicable describe the knowledge of the local study sites, culture, and society. Provide enough information so the IRB knows that you have qualified staff for the proposed research.

Note: If you specify a person by name, a change to that person will require prior approval by the IRB. If you specify people by role (e.g., coordinator, research assistant, Sub-Investigator, or pharmacist), a change to that person will not require prior approval by the IRB, provided that person meets the qualifications described above to fulfill their roles.

The investigators of this study are board-certified physicians and have all been involved in extensive clinical and basic science research. We have been through multiple IRB reviews. Our training is up to date. We have shown the highest ethical standard as recognized by our peers and institution while performing research projects.

a. Describe the availability of medical or psychological resources that subjects might need as a result of an anticipated consequences of the human research.

N/A

b. Describe your process to ensure that all persons assisting with the research are adequately informed about the protocol, the research procedures, and their duties and functions.

Once we have IRB approval for this project, investigators will meet to discuss the details of starting the study. Specific roles and tasks will be assigned by the principal investigator at that time.

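### Redo surgery, the event the trial is sized on, has no arm-neutral definition, no masked reading and no recorded indication, so a difference between arms could partly reflect different thresholds for reoperating

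*Combined protocol and SAP*

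**What the plan says.** - **Objective (section 1).** The trial is "to assess rate of recurrence of SDHs". Section 2 says the comparison will yield class I evidence. Recurrence is not defined.
- **Analysed event (9a).** The list of analysed variables includes "need for redo surgery for surgical decompression of SDHs", compared between arms by chi-square test. Follow-up CT findings are also compared by chi-square.
- **Sizing (9b).** "The sample size needed to examine differences in percent needing additional surgical decompression of SDH using a chi-square test" is the basis for 30 per group, with 35% assumed in controls. The table heads the same percentages as recurrence. The plan adds: "The expected percent needing additional surgical decompression of SDH in the treatment group is expected to be 5% or lower".
- **Who knows the arm (8b, 8d).** Investigators are given the random number list and assign patients from it. Controls have no embolization and no sham. In the text on managing procedural risk, 8d says: "Study investigators are experienced in performing the procedure and caring for the patients". Masking of patients, surgeons, CT readers or assessors is mentioned nowhere.
- **Imaging (8a).** Every patient has a CT within 24 hours of surgery and a standard CT at about 4-6 weeks. After that, "Further scans will be done thereafter if clinically indicated".
- **Data collected (8c, 9c).** The lists include GCS at admission and post-operative volume from CT, worded as IPH volume. They have no field for the indication for reoperation, neurological status at that time, or a subdural measurement before it. The principal investigator or study team enters the data from medical records (8d).

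**The concern.** That a second operation took place is a recorded fact. The decision to operate is a judgement, and the plan uses it to stand for recurrence. Take a patient with some re-accumulation on CT and mild symptoms. A surgeon who knows the vessel was embolized might wait, and one who knows it was not might reoperate. The same hematoma would then count as a success in one arm and a failure in the other.

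What is at stake is the meaning of a positive result. If the threshold differs between arms, fewer reoperations need not mean fewer recurrences, and the class I claim concerns the efficacy of embolization. The dataset as listed could not settle the matter afterwards, because it does not hold the reason for reoperating or the patient's state at that time. At 30 per arm, a few decisions can change the conclusion.

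**Working it through.** **1. The plan's own figure.** Inputs from 9a and 9b: alpha 0.05 (sidedness not stated), power 0.80, 0.85 and 0.90, control rate 35%, treatment rate 5% or 10%, equal groups. The usual two-proportion formula, two-sided and without continuity correction, is

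n = [1.960 × √(2p̄(1−p̄)) + z_power × √(p1(1−p1) + p2(1−p2))]² / (p1−p2)².

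For 35% versus 5% at power 0.80, p̄ = 0.20 and z_power = 0.842:

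n = [1.960 × √0.32 + 0.842 × √0.275]² / 0.30² = (1.109 + 0.441)² / 0.09 = 26.7, rounded up to 27.

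The remaining cells follow in the same way: 27/31/36 and 43/49/57, matching the table in all six. The formula gives 84.6% power at 30 per group for 35% versus 5%. The point is therefore not an arithmetic error.

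**2. How few events decide the result.** With 30 per arm and the uncorrected chi-square test:

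| Treatment reoperations | Fewest control reoperations for p < 0.05 |
|---|---|
| 1 | 6 |
| 2 | 8 |
| 3 | 10 |

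For 8 versus 2, p = 0.038; for 7 versus 2, p = 0.071. In that case one discretionary reoperation changes the conclusion. Near the planned rates the result is more robust: at 11 versus 2 (37% versus 7%), four fewer control reoperations are needed to lose significance.

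**3. What a threshold shift could do.** Suppose embolization has no effect. Let X and Y be the control and treatment reoperations, binomial with n = 30 and rates p1 and p2. Sum P(X = x) × P(Y = y) over all pairs with x > y and a chi-square p-value below 0.05. All rates below are assumptions.

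| Control | Treatment | Assumed shift | Significant in favour of embolization |
|---|---|---|---|
| 20% | 20% | none | 2.4% |
| 25% | 20% | 5 points, controls only | 6.5% |
| 22.5% | 17.5% | 2.5 points each way | 6.8% |
| 25% | 15% | 5 points each way | 15.5% |
| 27.5% | 12.5% | 7.5 points each way | 30.2% |
| 20% | 10% | 10 points, controls only | 19.3% (2.7% at 10% in both) |
| 40% | 30% | 5 points each way around 35% | 12.1% |

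Five points of 30 patients is 0.05 × 30 = 1.5 patients. A shift of 5 points each way is a 10-point gap, or 3 patients.

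**4. Search for a safeguard.** Section 10 has the monitoring board review whether repeat surgery is needed, but does not describe it as masked or as adjudicating events. Section 16 calls the neurosurgical service that assesses capacity a third party not associated with the study; it does not say that this service is unaware of the arm or applies a reoperation criterion. Section 8b promises equal follow-up care only during hospitalization and barring a complication.

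**The case against.** The strongest reply has four parts.

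- **Who decides is not stated.** No section says who decides on a redo operation. The sentence in 8d on investigators' experience does not give them that decision, and section 16 places at least part of the neurosurgical service outside the study. A reader might infer that investigators who expect a low treatment rate control the event. The documents do not support that as fact. Knowledge of the arm by treating clinicians remains a fair inference from the investigator-held list, the lack of any control procedure and the absence of a masking statement.
- **A less discretionary outcome is already planned.** Both arms have the 24-hour and 4-6 week CTs, and 9a compares CT findings. A reoperation difference without a CT difference might therefore show. This stands in part. Only scans after the 4-6 week CT are discretionary. However, a reoperation before that scan changes what it shows, 9a does not define the CT finding, and the volume field is not worded as a subdural measurement.
- **The illustration depends on its assumptions.** This stands. Shifts in both arms give larger figures than a shift in controls alone, and 20% is not a planning rate; it lies within the 5-30% recurrence range in section 2.
- **Unmasked care is common, and reoperation matters to patients.** This also stands. It is why reoperation should remain the event and why surgeons need not be masked. It does not explain leaving the counting rule and the indication unrecorded.

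**Conclusion.** The concern holds as a risk that the plan leaves open. The trial is sized and tested on redo decompression without an event criterion, masking of anyone, or a record of why patients were reoperated. If the plan is followed as written, a difference in reoperations cannot be separated from a difference in thresholds, and the class I claim is weakened to that extent.

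The size is illustrative: from 2.4% with no shift to 6.5% (25% versus 20%) or 15.5% (25% versus 15%), assuming no true effect, 30 per arm and the uncorrected chi-square test. A reader might take these as the trial's false-positive rate, or conclude that embolization would be favoured. Neither follows, because the documents show no shift, no size and no direction. Nor is the sample-size table at fault, since it reproduces exactly.

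**What to change.** Keep all reoperations as the event the trial is sized on, so that the basis for 30 per group is unchanged. Before enrolment:

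1. **Definition.** Add to 9a a definition of recurrence that is the same in both arms and does not depend on embolization status. The investigators set its clinical content. It governs what is counted, not when a surgeon operates.
2. **Record.** For each reoperation, add to the data collection form the indication, the neurological status and the subdural measurement on the CT before it.
3. **Masked measurement.** Have an existing team member without the assignment list measure the 24-hour CT, the 4-6 week CT and any CT before a reoperation, labelled by study ID only.
4. **Supporting analyses.** Prespecify two: reoperations that meet the definition; and recurrence meeting the definition on the last CT before reoperation or, otherwise, on the 4-6 week CT, whether or not the patient is reoperated.
5. **Interpretation.** State in advance that a reoperation result not matched by these analyses will not be described as class I evidence of reduced recurrence.

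The second supporting analysis should not replace the main event. It differs from the event behind the 35% and 5% assumptions. Beyond the scheduled CTs it could not be ascertained equally, because later scans are discretionary and participation runs from 2 weeks to 3 months (8e).

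The cost is protocol wording, a few form fields and some CT measurement time. Masking of CT reads and of neurological status may be imperfect, so the change reduces the problem without removing it.
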